2.2 Proximal Bronchial Tree Diagram (from RTOG 0236)

2.3 Staging Criteria

Patients will be staged according to the 7th edition of AJCC Cancer Staging Manual, 2010. See the staging reference in the Appendices.

3 Study Calendar

	Within 60	After	ARM	1 (SR)	ARM 2	(SBRT)				(From	B date o	OTH A f surge	RMS rv/end/	of SBR	T)			At time
days prior to reg. (except where noted)	reg. and before SBRT or surgery	At time of surgery	4 weeks post- op	Before final SBRT (same day)	4 weeks after SBRT	3 mo.	6 mo.	9 mo.	12 mo.	15 mo.	18 mo.	21 mo.	24 mo.	30 mo.	36 mo.	Yearly to 5 years	of disease relapse / PD	
Credentialing	x ¹																	
History & Physical, ECOG/Zubrod PS	Х			X		X	Х	Х	Х	Х	Х	Х	Х	Х	Х	Х	X	X
Pregnancy test	x ²																	
Tumor biopsy (and LN biopsy, if needed)	Х																	x ⁹
Pulmonary Function Tests	x ³						Х	Х		Х				Х				
PET/CT scan chest/upper abdomen	Х							Х		Х				Х		Х	Х	x ⁹
CT scan chest/upper abdomen				x ⁷			Х		Х		Х	Х	Х		Х			x ⁹
Adverse event assessment		X		Х		X	Х	Х	Х	Х								
Charlson Comorbidity Index		Х																
Blood specimen collection ⁴		x ⁵		X	X			Х		Х		Х		Х		Х	Х	
Tissue specimen collection ⁴			X															
EQ-5D, LCSS, LASA, UCSD SOB questionnaires		X		X		X	Х	X		X				Х				
QA submission to ITC		x ⁶		x ⁸		x ⁸												
Image submission to ITC																		x ⁹

1 Credentialing for surgery, brachytherapy, and SBRT may be completed any time prior to first registration. See Credentialing (Section 12).

2 For patients of childbearing potential.

3 Baseline PFTs are required within 90 days prior to registration. PFTs must include routine spirometry and DLCO. Arterial blood gases are not required but may be used as minor criteria for study enrollment. See Eligibility Criteria (Section 2.1).

4 Specimen collection is required for consenting patients only. See Biospecimen Collection (Section 13).

5 Pre-treatment blood specimen may be collected at the time of surgery for patients being treated on Arm 1.

6 Submission to ITC of the first patient's treatment plan is required prior to treatment for each type of SBRT system used at a site. See Quality Assurance Requirements (Section 5.4).

7 Post-implant CT scan is required for Arm 1 patients receiving brachytherapy.

8 See Quality Assurance Requirements (Section 5.4).

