5.4.3.1 Rapid Review of Treatment Plan for First Patient

Rapid review of the first patient's treatment plan prior to treatment is required for each type of SBRT system used at a site (e.g., Cyberknife, Linac-based, etc.).

The rapid review allows the study team to determine the institution's ability to generate a "per protocol" treatment plan. Each institution must digitally submit the planning CT dataset with the proposed treatment plan prior to the start of treatment for the first patient registered by the institution. The plan will be reviewed centrally by the study co-chair or designee, and suggestions regarding protocol compliance will be forwarded to the participating institution. Once the plan is approved, RTOG Headquarters will notify the site, and treatment may begin.

Prior to the start of SBRT, submit the following materials for the first patient treated with each type of SBRT system used at a site:

- Planning CT dataset (DICOM)
- Structure contours (DICOM RT Structure Set) for critical normal structures, all GTV, CTV, and PTV contours (C1, C3)
- Treatment plan (DICOM RT Plan) for initial and boost beam sets
- 3-D CALCULATED dose distributions (DICOM RT Dose) for initial and boost sets of concurrently treated beams
- Color isodose images in axial, sagittal, and coronal planes (JPEG or PNG screen captures)
- Digital DVH data for all required critical normal structures, GTV, CTV, and PTVs for total dose plan (DV)
- Online Digital Data Submission Information Form (DDSI) (available at http://atc.wustl.edu/forms/ddsi/ddsi.html).

The required imaging must be submitted digitally as DICOM RT. Submission by either CD or SFTP is supported. See QA Submission Instructions (Section 5.4.4).

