Severe pulmonary complications occur in about 10-20% patients after lobectomy, [42-48] 5-10% after SR, while grade \geq 3 radiation induced lung toxicity occurs in 10% patients treated with SBRT. [49-51] Currently, there are no means to predict which patient will develop such toxicity which patient will not. In general, the risk of pulmonary toxicity increases in patients with inadequate pulmonary function reserve, larger tumor size/larger treatment volumes, and use of chemotherapy. Many lung dosimetric factors, such as volumes receiving greater than certain dose (such as V30, V20, V13, and V5), the doses to a specific portions of the lung volume (such as D30), and mean lung dose (MLD) [52-59] were significantly associated with the risk of lung toxicity after radiation for populations of patients. However, a statistically significant association or description of complication rates for populations of patients is not the same as a good predictor for a given patient. For example, V13, V20, and MLD are significantly associated with radiation pneumonitis, but they all have a suboptimal predictive ability for individuals. [59] This is most likely from the complexity of underlying pathogenesis, which has not yet clearly defined, but apparently associated with involvements of multiple cytokines and yet to be defined signaling pathways. [60] Several reports have suggested a possible role of profibrogenic and proinflammatory cytokines in the modulation of radiation pulmonary injury including (by not limited to) Interleukin-1 (IL-1), IL-6, IL-8, IL-10, TNF-a, platelet-derived growth factor and Transforming growth factor beta 1 (TGF β 1).[61-69] Amongst these factors, TGF β 1, a prototype of multifunctional regulators of cell growth and differentiation produced by fibroblasts, macrophage and sometime tumor cells activated by ionizing radiation-induced free radicals, is the most extensively studied cytokine for radiation induced lung toxicity (RILT). TGFB1 stimulates connective tissue formation and decreases collagen degradation resulting in fibrosis and plays an important role in the inhibition of epithelial cell proliferation and the development of lung fibrosis associated with radiation pneumonitis and fibrosis. Researchers from Duke University reported that the plasma TGF^β level at the end of radiation correlated with symptomatic lung toxicity in patients treated with definitive radiation therapy. [70, 71] Kong et al. further demonstrated that the loss of mannose 6-phosphate insulin-like growth factor-2 receptor contributed to increased TGFB1 levels and subsequent radiation-induced pneumonitis in patients with NSCLC.[72] In patients treated with an escalated dose of radiation, Anscher et al. reported a significant correlation between TGF β_1 levels and late non-pulmonary grade ≥ 3 radiation toxicity.[73] Despite early controversial results on its predictive value in RILT, recent studies suggested that radiation-induced elevation of plasma TGFB1 at 4 weeks during the course of conventionally fractionated conformal radiation therapy is highly correlated with the occurrence of grade > 2 RILT.[61, 74] A combined analysis of University Michigan and Peking Union of Medical College further confirmed this finding, and combining TGF-B 1 and MLD can further stratify the risk of RILT.[75]

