Platelet-poor plasma will be obtained for cytokine and proteomic assays, serum samples will be used for metabolomics analysis. Buffy coat will be used for genomic studies. Plasma TGF- β 1 will be measured by molecular specific ELISA. The levels of other plasma cytokine will be measured by LINCOplex Kit (microsphere-based sandwich immunoassay) for the concentrations of proinflammatory cytokines, including G-CSF, IL-1 α , IL-1 β , IL-1 α , IL-6, IL-8, IP-10, MCP-1, MIP-1, TGF- α , and TNF- α) or other advanced kit with superior performance levels when they becomes available. RILT will be diagnosed and graded based on NCI's CTCAE. The plasma proteomes will be compared using a multiplexed quantitative proteomics approach involving ExacTag labeling, RP-HPLC and LC-ESI-MS/MS. Genomic studies such as single nucleotide polymorphism (SNP) studies will be performed using polymerase chain reaction (PCR) and allele specific primers. Since this is a prospective study, we anticipate advancement in experimental technology and preliminary results, other techniques and tests will also be applied if they are found them to be superior to the above stated ones.

Statistical Considerations

We recognize that almost all the data of the blood marker studies discussed above were related to RILT associated with conventionally fractionated radiation therapy. In this study, we hypothesized that severe pulmonary events from hypofractionated SBRT and surgical resection have a similar mechanism to that of RILT from 3DCRT. We will use logistic models to explore the relationship between grade \geq 3 pulmonary events and baseline levels of blood biomarkers of our interest (which may evolve with advances of technology and merging evidence) including (not limited to) TGF β 1, IL1, IL-6, IL-8 cytokine, SNPs of these cytokines and tPA, new proteomic makers prior to and during treatment. In addition, the Generalized Estimating Equation (GEE) method will be used to explore the relationship between treatment toxicities and marker levels measured during and after treatment. For proteomic analysis, variance components models will be used to identify the differential protein expression between patients with and without grade \geq 3 toxicity. Bioinformatic methodology may be applied for data analysis. As a secondary objective for toxicity study, we will also correlate blood based markers with grade \geq 3 non-pulmonary toxicities, which will also be defined by CTCAE.

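### The Hypothesis B marker models name no adjustment for baseline lung function, so a marker that only tracks poor lung function could be reported as a validated predictor of severe lung events

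*Combined protocol and SAP*

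**What the plan says.** Section 14.2.2, Statistical Considerations, sets out three kinds of model. For baseline markers: "We will use logistic models to explore the relationship between grade" 3 or higher pulmonary events and the marker levels. For later samples, GEE "will be used to explore the relationship between treatment toxicities and marker levels measured during and after treatment". For proteomics, variance components models comparing patients with and without severe toxicity. None names lung function, lung dose, tumour size or treatment arm. Each arm is split into 120 patients for discovery and 80 for blinded validation.

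The rationale in the same section says that "the risk of pulmonary toxicity increases in patients with inadequate pulmonary function reserve, larger tumor size/larger treatment volumes, and use of chemotherapy". It says that several lung dose measures (V20 and mean lung dose among them) "were significantly associated with the risk of lung toxicity after radiation for populations of patients", and it cites work in which TGF-beta1 combined with mean lung dose "can further stratify the risk of RILT". It also cautions that an association in a population does not make a good predictor for an individual.

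The Study Calendar (Section 3, footnote 3) states: "Baseline PFTs are required within 90 days prior to registration. PFTs must include routine spirometry and DLCO". In the SBRT arm the lungs must be contoured in every patient (5.3.8.3), and dose-volume data for the required normal structures go to the imaging QA center for every patient (5.4.3.1 and 5.4.3.2). In the SR arm, brachytherapy dose-volume histograms cover the target volumes and their expansions only (5.2.4).

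**The concern.** The objective (1.3.3) is to predict who is at high risk of pulmonary complications. Lung function is already known for each of these patients, so the useful question is whether a marker adds to it. A model with the marker alone cannot answer that. If a cytokine is higher in patients with poor reserve, and poor reserve raises the event rate, the marker will be associated with events even if it carries no information of its own.

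The training and test split guards against chance findings. It guards less well here, because the link between marker and lung function is present in both sets. At stake is a correlative report that presents, as a validated biomarker, something the baseline PFT already shows.

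**Working it through.** **1. The plan's own figure.** 120 + 80 = 200 per arm, which matches the roughly 200 per arm stated. The section gives no alpha, power, effect size or pass rule for this analysis.

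**2. Expected events.** The Hypothesis B rationale gives severe pulmonary events of 5-10% after SR and 10% after SBRT.
- Training: SR 120 x 0.05 to 0.10 = 6-12; SBRT 120 x 0.10 = 12; pooled 18-24.
- Test: SR 80 x 0.05 to 0.10 = 4-8; SBRT 80 x 0.10 = 8; pooled 12-16.

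**3. Simulation model.** L is standardised poor lung function. The marker is M = rho x L + sqrt(1 - rho^2) x noise, so it has no effect once L is known. Events follow logit P = a + ln(OR) x L, with a set to give 10% events overall. Two logistic models are fitted: M alone, and M plus L. A marker passes training if |z| > 1.96, and passes test if z > 1.645 in the same direction. There were 2,000 trials per setting. Rho, OR and both thresholds are assumptions. The GEE models were not simulated.

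**4. Hand check.** With M alone, the slope is about rho x ln(OR). For rho = 0.5 and OR = 2 this is 0.5 x 0.693 = 0.347. The expected z is about slope x sqrt(n x 0.10 x 0.90):
- pooled, n = 240: 0.347 x sqrt(21.6) = 0.347 x 4.65 = 1.61; chance of exceeding 1.96 is about 36%;
- one arm, n = 120: 0.347 x sqrt(10.8) = 0.347 x 3.29 = 1.14; chance about 21%.

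This is approximate and slightly high, because the true slope is a little below rho x ln(OR). It agrees in size with the simulation.

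**5. Results (% of trials in which the marker passes).**

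| Train/test | OR per SD | rho | Training, marker alone | Training, with L | Both sets, marker alone | Both sets, with L |
|---|---|---|---|---|---|---|
| 120/80 | 1.5 | 0.3 | 6.2 | 4.5 | 0.3 | 0.1 |
| 120/80 | 1.5 | 0.5 | 10.2 | 5.8 | 1.1 | 0.3 |
| 120/80 | 2.0 | 0.3 | 9.4 | 4.4 | 1.1 | 0.2 |
| 120/80 | 2.0 | 0.5 | 15.7 | 3.9 | 3.2 | 0.1 |
| 240/160 | 1.5 | 0.3 | 9.5 | 4.7 | 1.3 | 0.4 |
| 240/160 | 1.5 | 0.5 | 16.1 | 5.6 | 3.2 | 0.2 |
| 240/160 | 2.0 | 0.3 | 13.8 | 4.6 | 2.6 | 0.1 |
| 240/160 | 2.0 | 0.5 | 32.4 | 5.2 | 11.2 | 0.2 |

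The simulation error of a cell near 16% is sqrt(0.16 x 0.84 / 2000), or 0.8 points. Repeat runs moved single cells by up to about three points (the top per-arm training cell reached 19%, the lowest pooled one 7%). The conclusion therefore quotes 6-19% and 7-33% for training, and 0.5-4% and 0.7-11% for both sets. The repeat runs put the adjusted training rate at about 4-5%.

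**6. Sensitivity.** With rho = 0 the marker-alone rate is nominal (4-6%). At 5% events in the SR arm it is 5-10% in training and 0.3-1.6% through both sets. At the far end tried (rho 0.7, OR 3) it is 62% and 34% per arm, and 88% and 73% pooled.

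**The case against.** The plan is silent on covariates; it does not rule them out. The wording is exploratory and lets methods evolve, and Section 10.3.3 shows that the team uses patient covariates in adverse event models. A reader might infer that the models are fixed as marker only, but the text does not say so. Equally, the 10.3.3 clause is written for the treatment comparison of adverse events and PFTs, and nothing carries it into Section 14.2.

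A lung-function proxy does predict events in the crude sense, because the marginal association is real. The rates above are therefore not false positives for the question of whether the marker relates to events. They are errors only for the question of whether it adds to the PFT. This stands, and it limits the claim to added value.

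The test set also does much of the work: in the pooled setting with the strongest link, 32% falls to 11%. A reader might infer that such a marker would pass, or that validation gives no protection. Neither holds over the assumed range. An excess over the adjusted rate does remain.

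A reader might also infer that lung dose is missing from every model. Baseline markers are drawn before any dose is given and can relate to it only indirectly, for example through tumour size. No lung dose-volume data are requested for the SR arm. Dose matters mainly for SBRT markers measured during and after treatment.

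Finally, the aim is correlative, rests on optional specimens, and uses covariates that will be collected anyway, so adjustment can still be added before analysis. That lowers the urgency but does not remove the case for fixing the method in advance, since the section intends a validation claim.

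**Conclusion.** The point holds, with *could* rather than *would*. Section 14.2.2 names no adjustment for a risk driver that it identifies itself and that the trial measures in everyone. A marker with no information beyond lung function is significant in training in about 6-19% of cases per arm or 7-33% pooled, and passes both sets in about 0.5-4% or 0.7-11%. With lung function in the model the figures are about 4-5% and 0.4% or less. These are per-marker rates. They rest on an assumed correlation of 0.3-0.5, an odds ratio of 1.5-2.0 per SD, 10% events and 5% thresholds, and they shrink to nominal if either link is weak. The primary and secondary endpoints are not affected.

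**What to change.** In Section 14.2.2, keep the marker models and add:
- one pre-specified baseline PFT (DLCO or FEV1) in the logistic and GEE models;
- an arm term only where the arms are pooled, since it cannot be fitted within one arm;
- in the SBRT arm, one lung-dose measure (mean lung dose or V20), mainly for markers measured during and after treatment;
- for each marker, the likelihood-ratio gain over that clinical model in training and the change in discrimination in the test set.

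The cost is a few sentences and little analysis work, with no new data. The real constraint is events. With 12 training events in the SBRT arm, a marker, a PFT and a dose term leave 12 / 3 = 4 events per parameter, and the SR arm may have only 6 events. Keep to one or two covariates, and pool the arms or use a penalised fit. With 4-8 test events per arm (12-16 pooled), the change in discrimination will be imprecise and should carry a confidence interval.

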Т3	Tumor more than 7 cm or one that directly invades any of the following: parietal pleura (PL3) chest wall (including superior sulcus tumors), diaphragm, phrenic nerve, mediastinal pleura, parietal pericardium; or tumor in the main bronchus (less than 2 cm distal to the carina* but without involvement of the carina); or associated atelectasis or obstructive pneumonitis of the entire lung or separate tumor nodule(s) in the same lobe			
T4	Tumor of any size that invades any of the following: mediastinum, heart, great vessels, trachea, recurrent laryngeal nerve, esophagus, vertebral body, carina, separate tumor nodule(s) in a different ipsilateral lobe			
Nodal Inv	volvement (N)			
NX	Regional lymph nodes cannot be assessed			
NO	No regional lymph node metastases			
N1	Metastasis in ipsilateral peribronchial and/or ipsilateral hilar lymph nodes and intrapulmonary nodes, including involvement by direct extension			
N2	Metastasis to ipsilateral mediastinal and/or subcarinal lymph node(s)			
N3	Metastasis in contralateral mediastinal, contralateral hilar, ipsilateral or contralateral scalene, or supraclavicular lymph node(s)			
Distant Metastasis (M)				
MX	Distant metastasis cannot be assessed			
M0	No distant metastasis			
M1	Distant metastasis			
M1a	Separate tumor nodule(s) in a contralateral lobe, tumor with pleural nodules or malignant pleural (or pericardial) effusion**			
M1b	Distant metastasis			

16.2 Staging Reference (AJCC Cancer Staging Manual, 7th Edition, 2010)

* The uncommon superficial tumor of any size with its invasive component limited to the bronchial wall, which may extend proximal to the main bronchus, is also classified T1

** Most pleural (and pericardial) effusions associated with lung cancer are due to tumor. In a few patients, however, multiple cytopathological examinations of pleural (pericardial) fluid are negative for tumor, and the fluid is not bloody and is not an exudate. Where these elements and clinical judgment dictate that the effusion is not related to the tumor, the effusion should be excluded as a staging element and the patient should be classified as M0.

16.3 Stage Grouping

Stage	TNM
IA	T1a N0 M0
	T1b N0 M0
IB	T2a N0 M0
IIA	T2b N0 M0
	T1a N1 M0
	T1b N1 M0
	T2a N1 M0
IIB	T2b N1 M0
	T3 N0 M0
IIIA	T1a N2 M0
	T1b N2 M0
	T2a N2 M0
	T2b N2 M0
	T3 N1 M0
	T3 N2 M0
	T4 N0 M0
	T4 N1 M0
IIIB	T1a N3 M0
	T1b N3 M0
	T2a N3 M0
	T2b N3 M0
	T3 N3 M0
	T4 N2 M0
	T4 N3 M0
IV	Any T Any N M1a
	Any T Any N M1b

16.4 ECOG/Zubrod Performance Status Scale

- 0 Asymptomatic and fully active.
- 1 Symptomatic; fully ambulatory; restricted in physical strenuous activity.
- 2 Symptomatic; ambulatory; capable of self-care; more than 50% of waking hours are spent out of bed.
- 3 Symptomatic; limited self-care; spends more than 50% of time in bed, but not bedridden.
- 4 Completely disabled; no self-care; 100% bedridden.

16.5.1 Registration and Randomization

Registration is available 24 hours a day via the CTSU's Oncology Patient Enrollment Network (OPEN) Portal system. All participating sites (ACOSOG and non-ACOSOG sites) will use OPEN to enroll patients to this study. See Section 4.0.

16.5.2 Other Protocol Requirements

CTSU sites will follow the requirements of the protocol for all required procedures and submissions.
